10.2 ANALYSIS PLAN

Molecular Analysis

The analyses on molecular response will be performed on all patients with molecular data at a minimum of 2 post-baseline time points (HLA A2 positive patients must also have received at least 1 dose of the vaccine).

Immunological Analysis

To be evaluable for immunological response, positive HLA A2 patients must receive at least 1 dose of the vaccine and the immunological testing must be available until at least week 8 post first dose.

Safety Analysis

For safety analyses, all patients with positive HLA A2 status who received at least one study drug administration will be evaluable for toxicity. All controls will be included in the safety analyses, where relevant.

Other Analysis

For all other analyses, an intention to treat principle will be used.

10.2.1 ANALYSIS FOR CML PATIENTS ONLY:

Primary:

The primary endpoint is molecular response of BCR-ABL (major or minor response or CMR). For the purpose of analysis, response (as defined by section 9.6) will be measured at weeks 4, 8, 12, 16, 20, 32 and 11, 17 and 23 months. Fisher's exact test will be used to compare differences in proportions of molecular response in CML patients versus controls.

Secondary:

The primary analysis will be repeated for major response or CMR of BCR-ABL.

The analysis methods used for BCR-ABL will be repeated for WT1.

Progression free survival, duration of response and overall survival (as defined in Section 2.2) will be estimated using the method of Kaplan and Meier for each group. Survival estimates will be presented with 90% confidence intervals. These endpoints will also be compared between the CML patients and controls using log-rank tests.

Progression free survival for CML patients is defined in Section 2.2 and is measured as the time from date of consent to the study to date of progression or death from any cause. Alive patients who are progression free will be censored at their date of last follow up. Similar analysis will be performed for overall survival and duration of response.

Toxicity will be collected and evaluated according to the NCI CTC toxicity scale (v4.0) and compared between the vaccinated and control groups by Fisher's exact test.

10.2.2 ANALYSIS FOR AML PATIENTS ONLY:

Primary:

The primary endpoint is time to disease progression measured as the time from date of consent to the study to date of progression or death from any cause (progression is defined as disease relapse). Alive patients who are progression free will be censored at their date of last follow up. Progression free survival will be estimated using the method of Kaplan and Meier for each group. Survival estimates will be presented with 90% confidence intervals. A log rank test will be computed to compare AML patients and their controls.

Secondary:

The primary analysis will be repeated for survival time.

A secondary endpoint is molecular response of WT1 (major or minor response or CMR). For the purpose of analysis, response (as defined in section 9.6) will be measured at weeks 4, 8, 12, 16, 20, 32 and 11, 17 and 23 months. Proportions of responders in the vaccinated group will be compared with the control group using Fisher's exact test for the CML and AML groups. This analysis will be repeated for major molecular response or CMR of WT1.

Toxicity will be collected and evaluated according to the NCI CTC toxicity scale (v4.0) and compared between the vaccinated and control groups by Fisher's exact test.

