We propose to build on our established programme of DNA fusion gene vaccination delivered by intramuscular injection and exploiting our unique experience with electroporation, to induce durable immune responses with the aim of controlling disease by precision attack of the tumour by CD8+ T cells. The aim of the trial is to evaluate an identical vaccine strategy in two parallel settings with the purpose of identifying the most promising context for eventual phase III testing. We intend to test the hypothesis that molecular and clinical responses, induced by T cells can be predicted by increases in the number of CD8 T cells, specific for the vaccine-encoded T cell epitopes.

Studying two patient groups will maximise the knowledge gained from this vaccine trial: Patients with CML will allow a direct and objective assessment of the anti-leukaemia effect of vaccination at the molecular level by BCR-ABL and WT1 monitoring.

Patients with AML offer a difficult challenge to haematologists. The advantage of including this patient group is twofold. We can assess the anti-leukaemia effect of vaccination objectively by measuring WT1 gene expression levels. More importantly, we can gain data on the clinically highly relevant question of whether vaccination will prevent relapse in this patient group. Based on the MRC AML 11 trial data, it is anticipated that 60-75% of patients enrolled in this trial will relapse in 2 years (Figure 1) (25).

For both CML and AML the HLA A2 negative patients will be prospectively followed as control groups.

Figure 1. Survival and risk of relapse in AML

Overall survival (A) and relapse risk (B) in MRC AML11 trial are shown by hierarchical risk group. The risk groups were as follows. Favourable group: t(15;17), t(8;21), or inv(16), whether alone or in conjunction with other abnormalities. Intermediate group: normal karyotype, all other noncomplex abnormalities. Adverse group: complex karyotype (5 or more unrelated abnormalities), excluding cases with t(15;17), t(8;21), and inv(16).

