4 SELECTION AND WITHDRAWAL OF PATIENTS

4.1 INCLUSION CRITERIA

CML patients:

Philadelphia chromosome positive CML in chronic phase, in complete cytogenetic response (CCyR) but with detectable BCR-ABL transcripts and maintained the CCyR on tyrosine kinase inhibitor monotherapy for a minimum of 24 months

AML patients:

Patients with WT1+ AML complete remission (CR) post chemotherapy or AML in morphologic CR with incomplete blood count recovery (CRi) defined as patients who fulfil all of the criteria for CR except for residual neutropenia (<1,000/ μ L) or thrombocytopenia (<100,000/ μ L).

As the vast majority of AML express WT and evaluation in CR or CRi is technically not feasible, formal demonstration of WT1 expression in AML cells is not required. Where historical or relapsed samples become available, WT1 expression status will be evaluated post hoc.

All patients:

- ≥ 18 years of age,
- Written informed consent
- WHO Performance status of 0 or 1.
- For vaccination groups: HLA-A0201 positive in at least one allele
- For control groups: HLA A2 negative in both alleles
- Renal function and liver function (Creatinine <1.5 x upper limit of normal, liver function tests < 1.5 x upper limit of normal); Lymphocyte count 
> 1.0 x10⁹/l*; normal clotting
- HB>100 g/l
- Adequate venous access for repeated blood sampling according to protocol schedule.
- If sexually active and possibly fertile, patients must agree to use appropriate contraceptive methods during the trial and for six months afterwards.

* If the lymphocyte count is below 1.0 at the time of entry into the trial but has been over 1.0 in the last 6 months and has also not declined rapidly in the days and weeks preceding entry, then the patient is eligible.

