Given the funding envelope the study is begun under it is expected that the duration of the immunological evaluation of the study will extend beyond the evaluation of the primary endpoints and secondary endpoints. Immunological evaluation is also a rapidly changing field in which the tools are improved and newly developed quickly. To reflect this, in the consent form patients will be asked to permit this later use of material for additional immunological evaluations beyond the submission of the end of study report to the regulatory bodies.

9.6.1 MOLECULAR RESPONSE:

Definition of BCR-ABL Response

- For patients with a baseline BCR-ABL transcript level less than 11: CMR: 0 BCR-ABL transcript level with ABL control copy greater than or equal to 32,000; in TWO CONSECUTIVE tests. These patients cannot be assessed for a major or minor response as defined below.
- 2) For patients with a baseline BCR-ABL transcript level greater than or equal to 11:
 - a. CMR: 0 BCR-ABL transcript level with ABL control copy greater than or equal to 32,000; in TWO CONSECUTIVE tests.
 - b. Major response: a fall greater than 1 log in the BCR-ABL transcript level ratio.*
 - c. Minor response: a fall greater than 0.5 log in the BCR-ABL transcript level ratio.*

*Confirmed in an ABL control copy greater than or equal to 32,000 in two consecutive samples at any time during follow up.

Definition of WT1 Response

1) For patients with a baseline WT1/GUS ratio less than 0.1%:

CMR: 0% WT1/GUS ratio with GUS control copy greater than or equal to 32,000; in TWO CONSECUTIVE tests.

These patients cannot be assessed for a major or minor response as defined below.

- 2) For patients with a baseline WT1/GUS ratio greater than or equal to_0.1%:
 - a. CMR: 0% WT1/GUS ratio with GUS control copy greater than or equal to 32,000; in TWO CONSECUTIVE tests.
 - b. Major response: a fall greater than 1 log in the WT1/GUS ratio.*
 - c. Minor response: a fall greater than 0.5 log in the WT1/GUS ratio.*

*Confirmed in a GUS control copy greater than or equal to 32,000 in two consecutive samples at any time during follow up.

9.6.2 IMMUNOLOGICAL RESPONSE:

Definition of validated assay by ELISPOT response:

A positive response using the validated assays by ELISPOT will be determined by having all of the following criteria:

- More than 25 spots per million Peripheral Blood Mononuclear Cell (PBMC) assay;
- (increase in spot number exceeds spot number at baseline + 2 x standard deviation at baseline;

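### The AML WT1 response endpoint (secondary) pools patients who can show a log fall with patients who can respond only by CMR, and counts unchanged 0% WT1 as a response

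*Protocol*

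**What the plan says.** Section 2.2.2 lists WT1 molecular response among the AML secondary endpoints. Section 10.2.2 repeats this ("A secondary endpoint is molecular response of WT1 (major or minor response or CMR") and gives the test: "Proportions of responders in the vaccinated group will be compared with the control group using Fisher's exact test for the CML and AML groups". The analysis is then repeated for major response or CMR.

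The denominator comes from the molecular analysis paragraph of section 10.2: "The analyses on molecular response will be performed on all patients with molecular data at a minimum of 2 post-baseline time points". Vaccinated patients must also have had at least one dose. Baseline WT1 plays no part.

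Section 9.6.1 defines WT1 response in two strata.

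- **Baseline below 0.1%** ("For patients with a baseline WT1/GUS ratio less than 0.1" per cent). The only route is complete molecular response: "CMR: 0% WT1/GUS ratio with GUS control copy greater than or equal to 32,000; in TWO CONSECUTIVE tests". The protocol adds: "These patients cannot be assessed for a major or minor response as defined below".
- **Baseline 0.1% or above.** The routes are the same CMR, a fall of more than 1 log (major) or a fall of more than 0.5 log (minor), the falls confirmed in two consecutive adequate samples.

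Under section 4.1, AML patients enter in CR or CRi. No WT1 level is required at entry, and section 4.2 does not exclude an AML patient whose WT1 is already 0%.

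**The concern.** The response definition and the analysis set do not fit together. Section 9.6.1 recognises that a log fall cannot be scored from a very low baseline. Section 10.2 then puts those patients in the same responder proportion as patients who can show a fall.

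Two things follow. Where low-baseline patients do not reach CMR, they dilute the comparison. Where they do, the response may reflect no change at all: CMR is an absolute level, so a patient at 0% at baseline and at two later tests is a responder whether vaccinated or not. Such responses add to both arms and blur any difference.

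The CML side shows the contrast. For BCR-ABL, section 4.1 requires detectable transcripts and section 4.2 excludes CMR, so an unchanged zero cannot be scored as a BCR-ABL response. AML has no parallel condition on WT1.

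In addition, the protocol defines no outcome for a WT1 rise. Under the response definition, a patient whose WT1 climbs from a measurable baseline and one whose WT1 stays flat are both non-responders.

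At stake is the reading of the AML molecular comparison. A null result could come from the mix of baselines, and a high response rate could come from patients who were negative throughout.

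**Working it through.** **The plan's own figure.** The AML design in section 10.1.2 concerns 2-year PFS, not WT1. It reproduces exactly. With X ~ Binomial(39, p) and success at X ≥ 16, P(X ≥ 16 | p = 0.30) = 0.0944 and P(X ≥ 16 | p = 0.50) = 0.9002, against stated limits of 10% for each error. The protocol states no rate or power for the WT1 endpoint, so no stated number is wrong. What follows is an illustration.

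**Inputs**

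- Vaccinated patients: 39 (section 10.1.2).
- Controls: 39, assumed. Section 3 does not fix the control number.
- Share g with baseline WT1/GUS ≥ 0.1%: not given; taken as 1, 0.5 and 0.3.
- Response among those patients: 40% v 5%, assumed.
- CMR probability c among low-baseline patients, the same in both arms: not given; taken as 0, 25% and 50%.
- Two-sided Fisher's exact test at 5%, assumed. Power is counted where the vaccine arm is better.

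**Formulas**

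- All patients, 39 v 39: vaccine rate = 0.40g + c(1 − g); control rate = 0.05g + c(1 − g).
- Restricted to baseline ≥ 0.1%: n = round(39g) per arm, rates 40% v 5%.
- Power = sum of the two binomial probabilities over all outcomes (x, y) with a higher vaccine proportion and Fisher p ≤ 0.05.

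**Results**

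| g | c | Pooled rates | Power, all patients | Power, restricted |
|---|---|---|---|---|
| 1 | – | 40% v 5% | 97% | 97% (39 v 39) |
| 0.5 | 0 | 20% v 2.5% | 58% | 72% (20 v 20) |
| 0.5 | 25% | 32.5% v 15% | 35% | 72% |
| 0.5 | 50% | 45% v 27.5% | 27% | 72% |
| 0.3 | 0 | 12% v 1.5% | 21% | 36% (12 v 12) |
| 0.3 | 25% | 29.5% v 19% | 13% | 36% |
| 0.3 | 50% | 47% v 36.5% | 11% | 36% |

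At g = 0.5 and c = 0.25, for example, the vaccine rate is 0.40 × 0.5 + 0.25 × 0.5 = 0.325 and the control rate is 0.05 × 0.5 + 0.25 × 0.5 = 0.15.

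**How much the denominator rule costs.** With c = 0, restriction recovers 72 − 58 = 14 points at g = 0.5 and 36 − 21 = 15 points at g = 0.3. The rest of the fall from 97% comes from having fewer patients in whom a fall can be seen, and no choice of denominator restores it. With CMR unrelated to the vaccine at 25% to 50%, restriction recovers 37 to 45 points at g = 0.5 (72 − 35 and 72 − 27).

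**The opposite case.** Suppose low-baseline CMR is vaccine-driven. At g = 0.5 with CMR of 20% v 5%, the pooled rates are 0.5 × 40% + 0.5 × 20% = 30% and 5%, and all-patient power is 81%. With CMR of 40% v 5%, the pooled rates are 40% v 5% and power is 97%. Both exceed the restricted 72%.

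**The case against.** The strongest reply is that the low-baseline patients are not unassessable. Section 9.6.1 closes only major and minor response to them and gives them CMR, which is part of both AML WT1 analyses. Keeping them in the denominator follows from the definition. This stands: a reader might infer that the endpoint scores only falls, or that these patients are automatic non-responders, and neither is so. It does not remove the point, because this one open route needs no change from baseline.

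A reader might also infer that the AML cohort cannot show what the vaccine is for. The documents do not support that. Section 1.1.3 asks "whether vaccination will prevent relapse in this patient group", and the AML primary endpoint, time to relapse or death, tests this directly, with 2-year PFS as a further secondary endpoint. The WT1 endpoint does not enter the AML sample size or decision rule.

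Section 4.1 says of WT1 that "evaluation in CR or CRi is technically not feasible", and a reader might take this as an admission that baseline WT1 is uninformative. In context it explains why WT1 expression in AML cells need not be shown at entry. It is not about the blood qPCR, which section 1.1.3 presents as a standardised marker of residual disease.

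The power figures rest wholly on assumptions, and the protocol claims no power here. That stands too. Further analyses of the WT1 series, including a rise, may be in a statistical analysis plan that is not shown. The absence of a rise outcome is therefore a remark, and a remedy for it is optional.

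**Conclusion.** The point holds for a secondary endpoint. Taken together, sections 9.6.1, 10.2 and 10.2.2 put two groups with different routes to response into one Fisher comparison, and they allow a patient at 0% WT1 from baseline onwards to count as a responder in either arm.

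The size is unknown, because the protocol gives neither the share below 0.1% nor the share at 0%. With half of 39 per arm assessable and 40% v 5% among them, all-patient power is 58% without low-baseline CMR and 35% to 27% with 25% to 50% CMR in both arms, against 72% when restricted. These figures depend on the assumed rates, control number, 5% level and a CMR rate unrelated to the vaccine; if CMR in low-baseline patients were truly vaccine-driven, the all-patient analysis would be the more powerful one. The case for changing the main comparison is therefore mainly one of interpretation, with power as a likely but not certain gain. The primary AML analysis is unaffected.

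**What to change.** In section 10.2:

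1. Make the AML WT1 response comparison (major, minor or CMR) among patients with baseline WT1/GUS of 0.1% or above.
2. Report CMR in patients below 0.1% separately, by arm, and only for those with a non-zero baseline.
3. Keep the all-patient comparison as supportive, which covers the case of a vaccine effect on low-baseline CMR.

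Optionally, as exploratory for AML, add time to a confirmed WT1 rise, compared at the visits both arms attend. Its threshold should be fixed before the data are seen and should not be met by a trivial crossing of 0.1%, such as 0.09% to 0.11%.

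The change is to analysis wording only; the samples, assay and baseline values are already scheduled. The price is fewer patients in the fall-based comparison, for example 20 v 20 in place of 39 v 39 if half are assessable.

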2.2 SECONDARY ENDPOINTS

2.2.1 CML:

- 1) Molecular response of BCR-ABL (major response or CMR, as defined in Section 9.6).
- 2) Molecular response of WT1 (major or minor response or CMR, as defined in Section 9.6).
- 3) Time to disease progression. Disease progression for CML patients is defined as a loss in complete haematological response, where at least one factor falls out of the following ranges (81):
 - WBC < 10×10^9 /L
 - Basophils < 5%
 - No myelocytes, promyelocytes, myeloblasts in the differential
 - Platelet count < 450 x 10^9 /L

- Spleen nonpalpable
- 4) Time to next treatment. A next treatment is defined as the first drug taken during the course of the study with an indication to treat CML.
- 5) Duration of molecular response:
 - a. Measured from the beginning of tyrosine kinase inhibitor treatment.
 - b. Measured from the time of obtaining informed consent
- 6) Overall survival.
- 7) Toxicity assessed according to NCI CTCAE v4.0.
- 8) Pain assessment immediately after vaccination
- 9) Pain assessment at 48 hrs post vaccination

2.2.2 AML:

- 1) 2 year overall survival
- 2) 2 year progression free survival.
- 3) Overall survival.
- 4) Molecular response of WT1 (major or minor response or CMR, as defined in section 9.6).
- 5) Toxicity assessed according to NCI CTCAE v4.0
- 6) Pain assessment immediately after vaccination
- 7) Pain assessment at 48 hrs post vaccination

2.2.3 HLA A2 positive patients only (CML and AML):

- 1) Immune response to WT1-epitope specific T cells in blood and/or bone marrow, using validated assays by ELISPOT and/or ICS and tetramer staining. A positive response using the validated assays by ELISPOT is defined in Section 9.6.
- 2) Number of WT1 specific T-cells after peptide challenge to the skin (wherever assessment is feasible).
- 3) Immune response to DOM, using validated assays by ELISA.
- 4) Immune response to DOM specific T cells, using validated assays by ELISPOT.
- 5) Number of humoral responses (B-cells) to the vaccine components, by ELISA.

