10 STATISTICS AND DATA ANALYSIS

10.1 SAMPLE SIZE CALCULATION

10.1.1 SAMPLE SIZE CALCULATION FOR CML

The sample size calculation is based on A'Hern's Single-Stage Design and the primary outcome measure of molecular response (BCR-ABL or WT1).

A molecular response (BCR-ABL or WT1) rate of 20% would imply the vaccine clearly warrants further investigation. A molecular response rate of 5% or less would be unacceptable and would indicate the vaccine does not warrant further investigation. The probability of obtaining a false positive result, α (i.e. incorrectly accepting for further study a treatment that has a true PFS rate 30%) is set at 10%. The probability of a false negative result, β (i.e. incorrectly rejecting for further study a treatment with a true PFS rate of 50%) is set at 10%. Using these parameters, $\alpha = 0.1$, $\beta=0.1$, p0=5%, p1=20%, 32 HLA A2+ve patients need to be recruited to the study. The drop-out rate is expected to be less than 10%, hence a total of 36 patients will be recruited.

This trial needs to observe a minimum of 4 out of 32 patients who are molecular responders in order to provide evidence that the vaccine warrants further investigation. Patients will be followed up for 2 years to assess molecular response.

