10.1.2 SAMPLE SIZE CALCULATION FOR AML

The sample size calculation is based on A'Hern's Single-Stage Design and the primary outcome measure of progression free survival (PFS) at 2 years.

A progression free survival rate of 50% at 2 years would imply the vaccine clearly warrants further investigation. A PFS rate of 30% or less at 2 years would be unacceptable and would indicate the vaccine does not warrant further investigation. The probability of obtaining a false positive result, α (i.e. incorrectly accepting for further study a treatment that has a true PFS rate 30%) is set at 10%. The probability of a false negative result, β (i.e. incorrectly rejecting for further study a treatment with a true PFS rate of 50%) is set at 10%. Using these parameters, $\alpha = 0.1$, $\beta=0.1$, p0=30%, p1=50%, 39 HLA A2+ve patients need to be recruited to the study. The drop-out rate is expected to be less than 10% (see section 3.1 for details of patient replacement).

This trial needs to observe a minimum of 16 out of 39 patients who are progression free and alive at 2 years in order to provide evidence that the vaccine warrants further investigation.

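### Both cohorts are sized on a single-arm A'Hern rule, but section 10.2 labels comparisons with an unsized control group as primary and never mentions that rule

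*Protocol*

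**What the plan says.** **Sizing.** Section 3 says that the HLA A2+ group was sized by A'Hern's single-stage design, and that the controls are all eligible, consenting HLA A2-negative patients. No control number is given.

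- CML (10.1.1): "The sample size calculation is based on A'Hern's Single-Stage Design and the primary outcome measure of molecular response (BCR-ABL or WT1"), with "p0=5%, p1=20%, 32 HLA A2+ve patients need to be recruited to the study", alpha 0.1 and beta 0.1. The go rule is: "This trial needs to observe a minimum of 4 out of 32 patients who are molecular responders".
- AML (10.1.2): 2-year PFS is called the primary outcome measure, with p0 30%, p1 50%, alpha 0.1 and beta 0.1. The go rule is: "This trial needs to observe a minimum of 16 out of 39 patients who are progression free and alive at 2 years".

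**Analysis.** Under the primary heading for CML (10.2.1), Fisher's "exact test will be used to compare differences in proportions of molecular response in CML patients versus controls". Under the primary heading for AML (10.2.2), PFS is estimated by Kaplan-Meier in each group with 90% confidence intervals, and "A log rank test will be computed to compare AML patients and their controls". Neither 4/32 nor 16/39 appears in 10.2, and neither test has a stated level, sidedness or power.

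**Endpoints.** Section 2.1.2 makes time to progression the AML primary endpoint, and 2.2.2 lists "2 year progression free survival" as secondary. For CML, 2.1.1 and 10.2.1 use BCR-ABL response alone.

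**The concern.** The error rates in 10.1 are properties of a count in the vaccinated arm. The analyses that 10.2 calls primary are between-group tests, whose power depends on a control number the protocol leaves open. The stated 90% power is therefore not the power of those tests.

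The two approaches can also give different answers on the same data. A cohort that meets its count can show an unremarkable comparison with controls, and the protocol does not say which result is the primary one. This matters because section 1.1.3 says the aim is to identify the more promising setting for phase III testing. For AML, the sections also disagree on which endpoint is primary.

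**Working it through.** **1. Reproduce the plan's own figures.** Inputs are from 10.1.1 and 10.1.2. With X binomial(n, p), alpha = P(X ≥ r | p0) and power = P(X ≥ r | p1).

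| Cohort | n, r | p0, p1 | Exact alpha | Exact power |
|---|---|---|---|---|
| CML | 32, 4 | 5%, 20% | 7.4% | 90.7% |
| AML | 39, 16 | 30%, 50% | 9.4% | 90.0% |

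A search for the smallest n with alpha ≤ 10% and power ≥ 90% returns (32, 4) and (39, 16), as stated. The sizing is correct for a single-arm rule.

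**2. Power of the CML Fisher test.** Assumptions: 32 vaccinated patients at 20%, and controls at 5% (the design's p1 and p0). Power is the sum, over all pairs (x, y), of binomial(x; 32, 0.20) × binomial(y; m, 0.05) where Fisher's p is at or below the level. The control number m and the level are assumptions.

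| Controls m | two-sided 5% | two-sided 10% | one-sided 10% |
|---|---|---|---|
| 16 | 15% | 24% | 35% |
| 32 | 28% | 40% | 61% |
| 64 | 56% | 68% | 73% |
| 96 | 65% | 73% | 77% |

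**3. Power of the AML log-rank test.** Assumptions: exponential PFS, 50% v 30% at 2 years, 39 vaccinated patients, everyone followed for 2 or 3 years.

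- Hazard ratio = ln(0.5)/ln(0.3) = 0.576, and |ln HR| = 0.552.
- Events at 2 years with 39 controls: 39 × 0.5 + 39 × 0.7 = 46.8. At 3 years: 39 × (1 − 0.5^1.5) + 39 × (1 − 0.3^1.5) = 57.8.
- Schoenfeld: z = 0.552 × √(events × ½ × ½) = 1.89 at 2 years and 2.10 at 3 years. Power = Φ(z − z_crit).

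| Controls | two-sided 5% | two-sided 10% | one-sided 10% |
|---|---|---|---|
| 20 | 33-39% | 45-52% | 59-66% |
| 39 | 47-56% | 60-68% | 73-79% |
| 78 | 61-70% | 72-80% | 83-88% |
| 120 | 68-76% | 78-85% | 87-92% |

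Each range runs from 2 to 3 years of follow-up. Simulation with 20, 39, 60 and 78 controls agreed to within about 5 points. In the scenarios tried for both tests, 90% is reached only by the log-rank at one-sided 10% with 120 controls and 3 years.

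**4. How often the CML results would disagree.** If the true rates are 20% v 5%, the probability of meeting 4/32 while missing Fisher significance is:

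- 63% (32 controls) and 35% (64 controls) at two-sided 5%;
- 30% and 18% at one-sided 10%.

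As an example, 4/32 v 2/40 meets the rule with Fisher p = 0.40 (one-sided 0.24).

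**5. What the control group can add.** Section 1.1.3 says that "it is anticipated that 60-75% of patients enrolled in this trial will relapse in 2 years". That implies an untreated 2-year PFS of at most 25-40%, since deaths in remission also count as events. P(X ≥ 16 | 39, p) is 2%, 9%, 26% and 51% at p = 25%, 30%, 35% and 40%. The assumed p0 of 30% lies inside the range, but the false-positive rate of the AML rule moves a good deal with it.

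**The case against.** The best defence is that 10.1 already fixes the decision. Only the A'Hern counts are tied to a conclusion about further investigation; the Fisher and log-rank tests carry no level, power claim or go rule. On that reading 10.1 decides and 10.2 reports. This has force: a reader might infer that the trial has no pre-set decision rule, and that would be wrong. But the reading has to be supplied, because 10.2 labels the control comparisons primary without mentioning the counts. The AML conflict between 10.1.2, 2.1.2 and 2.2.2 remains either way.

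Three other stronger readings are not supported:

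- A reader might infer that the primary analyses simply have about 30-60% power. That range needs roughly 1:1 controls and a two-sided 5% test, and the protocol states neither. At one-sided 10%, the level built into the A'Hern design, 1:1 gives 61% and 73-79%. More controls raise the power further.
- A reader might infer that the AML primary analysis is only a log-rank test. Section 10.2.2 also gives Kaplan-Meier PFS per group, from which the vaccinated group's 2-year PFS can be read. It does not link that estimate to 16/39.
- A reader might fault a 90% interval for the CML response rate because, at 4/32, it would include 5%. No such interval is planned; the 90% intervals are for survival estimates.

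The test level and sidedness may be in an SAP that is not at hand, so their absence is not itself the finding. The conflict over which endpoint and analysis are primary is within the protocol.

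**Conclusion.** The point holds as an internal contradiction about the primary analysis in both cohorts and about the primary endpoint in AML. That part rests on the text alone. The A'Hern sizes and cut-offs are right, but their 90% power belongs to a rule that 10.2 does not carry.

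The size of the shortfall is conditional. With 1:1 controls it is 28% (Fisher) and 47-56% (log-rank) at two-sided 5%, and 61% and 73-79% at one-sided 10%. Across 16 to 96 CML controls and 20 to 120 AML controls, and the three levels shown, the span is 15-77% and 33-92%. These figures take the design's p0 and p1 as the true group rates and, for AML, exponential PFS.

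A related mismatch needs settling at the same time. The CML rates and the 4/32 rule are set for BCR-ABL or WT1 response, while the primary endpoint is BCR-ABL alone.

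**What to change.** 1. In 10.2.1 and 10.2.2, name the exact single-arm rule in HLA A2+ patients (at least 4/32; at least 16/39 progression free and alive at 2 years) as the primary analysis to which alpha = beta = 10% apply.
2. In 2.1.2, make 2-year PFS the AML primary endpoint, and remove it from the secondary list in 2.2.2.
3. Reconcile the CML endpoint. Either state in 10.1.1 that the 5% and 20% rates and the 4/32 rule apply to the BCR-ABL endpoint of 2.1.1, or restate the rates and rule. Step 1 should not be adopted for CML until this is settled.
4. Label the Fisher and log-rank comparisons as supportive, with no power claim, and report the control-group rate beside p0 as a check on it.

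The cost is amendment wording, with no change in sample size and no data lost. The small downside is that the control comparison loses its primary label; step 4 keeps its value as a guard against a wrong p0.

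Keeping the comparison as primary would be much dearer. At 1:1, 90% power and two-sided 10%, CML would need 82 patients per arm (95 with continuity correction), and AML would need 113 events: about 190 patients in total with 2 years of follow-up, or 153 with 3.
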